		Section 7.10 The 'Assessment windows and analysis visits' section was substituted by 'Analysis visits' section. Assessment windows are disregarded in current version and the main difference in analysis windows approach is that:  nominal (actual) visit dates will be used as per eCRF,  unscheduled visits for visit-based analyses will be disregarded, except baseline assessment  unscheduled visits will be considered only for patient data listings and spaghetti plots	Applying the assessment windows clarifies the approach for using unscheduled visit data.
		Section 9.6.1 Categories of exposure duration and the cumulative exposure duration were defined based on study days	This approach enables an easier interpretation of the results
		Section 10.2 Spaghetti plots for % change from baseline for each subject were added	These plots will allow detailed exploration of the results

Version	Date	Changes	Rationale for Change
		All plots will be produced also for Urine creatinine parameter	
		Section 10.3 Analysis of Proteinuria response will be evaluated also on PPS population	UPCR is an important efficacy endpoint and the analyses done on PPS population will allow detailed interpretation of the results
		Section 10.4 Analysis of Renal Function assessed by eGFR will be evaluated also on PPS population	Renal Function is an important efficacy endpoint and the analyses done on PPS population will allow detailed interpretation of the results
		Section 10.4 The eGFR will be evaluated as % change from baseline to each visit until End of Study.	No sense from clinical point of view doing the evaluation from EOT until EOS
		Section 10.5 The serum albumin levels will be evaluated as % change from baseline to each visit until End of Study.	No sense from clinical point of view doing the evaluation from EOT until EOS
		Section 10.7 Number (%) of subjects with doubling of serum creatinine either vs. baseline or any nadir measured during the trial was removed from the analyses	Is not needed per Protocol
		Section 10.8 The kidney specific subscales will be derived using additional SAS code (Appendix 1).	The evaluation of kidney specific subscales is not included in core scoring software provided by Optum
		Section 10.9 The kinetics of anti-PLA2R titers will be evaluated as % change from baseline to each visit until End of Study.	No sense from clinical point of view doing the evaluation from EOT until EOS

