## 7.10. Analysis visits

For parameters that will be summarized by visit, the nominal visit as recorded in the eCRF (i.e. actual visit date) will be used (disregarding the allowed assessment windows). Data collected in unscheduled visits will be displayed in patient data listings and spaghetti plots only, except Baseline assessment (refer to section 7.7). The unscheduled visit results will be flagged in the listings accordingly and will be highlighted by asterisks on spaghetti plots.

In the case of multiple records for one visit, selection rules are described in section 7.11 (below).

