### 7.13.3. Overall response for subjects

#### Immunological Response

Immunological responses are reflected by the reduction of anti-PLA2R antibody titres as measured by ELISA (Euroimmun). Based on the immunological responses, the following response categories are defined for this clinical trial (the baseline value is the last measurement obtained prior to treatment start):

- Immunological Partial Response (IPR): Reduction of anti-PLA2R antibody titres by at least 50% compared to baseline
- Immunological Complete Response (ICR): Reduction of anti-PLA2R antibody titres to less than 14.0 RU/mL
- Stringent Immunological Complete Response (sICR): ICR and a negative result in anti-PLA2R immunofluorescence test

The following variables related to immunological responses are defined as follows.

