## STATISTICAL ANALYSIS PLAN

MorphoSys AG  
MOR202C103

- Time to First Immunological Response (in months) prior to start of prohibited treatment (see definition in section 7.13.6) or progression, defined as  
[Date of first documented response of IPR, ICR or sICR (whichever is earlier) – Start date of study drug + 1 day]/30.4375
- Best overall immunological response (BIR) is defined when a subject is classified as having a IPR, ICR, or sIRC at any time during the trial but prior to start of prohibited treatment or progression. Responses for BIR are ordered as IPR < ICR < sICR. If a subject meets the criteria for more than one response category, the subject will be classified in the highest category.
- Time to BIR (in months), defined as  
[Date of BIR – Start date of study drug + 1 day]/30.4375
- Duration of Immunological response (in months), defined as  
[Date of death, PD or start of prohibited treatment (whichever is earlier) – Date of first documented response of IPR, ICR or sICR (whichever is earlier) + 1 day]/30.4375. Subjects with a response but no date of death, PD or start of prohibited treatment at the time of analysis cut-off will be censored at the date of last response assessment. Subjects without a response of IPR, ICR or sICR are assigned a duration time of zero.

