## 10. EFFICACY ANALYSIS

For the primary completion analysis, the analyses will be performed based on the visits during the safety run-in phase and treatment phase.

For the final analysis, the analyses will be performed based on all the visits during the trial.

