**Table 3. Allowed assessment windows.**

Visit	Target day	Analysis Window
1 week	Day 7	Day 2 to Day 10
2 weeks	Day 14	Day 11 to Day 17
3 weeks	Day 21	Day 18 to Day 26
1 month	Day 30	Day 27 to Day 45
2 months	Day 61	Day 46 to Day 75
3 months	Day 92	Day 76 to Day 107
4 months	Day 122	Day 108 to Day 138

6 months	Day 183	Day 139 to Day 229
9 months	Day 274	Day 230 to Day 320
12 months	Day 366	≥ Day 321

The closest value to the target day should be taken into analysis. If there are two values equidistant from the target date, then the latest value will be taken in the analysis. Unscheduled visits are considered in sensitivity analysis.

The sensitivity analyses will be applied to the following endpoints:

Best immunological response rate, section 10.1

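### SAP 7.10 and 10.10 imply that unscheduled post-baseline results stay out of the main response and progression derivations, although both endpoints are defined as occurring at any time

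*SAP*

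**What the plan says.** **The restriction.** SAP 7.10 opens with a scope sentence: "For parameters that will be summarized by visit, the nominal visit as recorded in the eCRF (i.e. actual visit date) will be used". It then says of unscheduled data: "Data collected in unscheduled visits will be displayed in patient data listings and spaghetti plots only, except Baseline assessment". SAP 10.10, below its window table, adds: "Unscheduled visits are considered in sensitivity analysis". BIRR is among the endpoints that this sensitivity analysis covers.

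**The definitions.** SAP 7.13.3 assigns BIR to a subject who reaches a response category "at any time during the trial but prior to start of prohibited treatment or progression". Protocol 12.9 likewise sets no visit limit. The lowest category, immunological partial response (IPR), requires: "Reduction of anti-PLA2R antibody titres by at least 50% compared to baseline". The SAP 10.1 table counts subjects with PD at any time in the trial. SAP 7.13.4 defines PD without a confirmation rule, and SAP 7.13.5 takes the first documented PD as the event date. None of these places limits the source to scheduled visits.

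**The analysis periods.** SAP 10 states: "For the final analysis, the analyses will be performed based on all the visits during the trial". For primary completion, "the analyses will be performed based on the visits during the safety run-in phase and treatment phase".

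No visible text says which records feed the main BIR and PD derivations.

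**The concern.** Two programmers working from the same SAP could classify one subject differently. One follows 7.13.3 to 7.13.5 and uses every result. The other follows 7.10 and uses scheduled visits only.

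PD matters most, because it has three roles. It is counted in the key secondary table. It ends the period in which a response can count and censors time to response. Under Protocol 8.8.2 it also ends MOR202 treatment. A subject could therefore stop treatment for a PD found at an unscheduled visit, yet have no PD in the efficacy analysis and be censored in time to PD. The disposition and efficacy tables of the same report would then disagree.

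BIRR is the key secondary endpoint, and here too the outcome would depend on the section followed. In addition, the main and sensitivity versions of BIRR would differ partly for a reason unrelated to the exclusions that the sensitivity analysis is meant to test.

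**Working it through.** **1. The plan's own figures.** No figure is stated for BIRR or PD. The only design calculation (Protocol 12.5, SAP 6.3) is the chance of seeing at least one adverse event: 1 − 0.90^20 = 87.8% against the stated 88%, and 1 − 0.85^10 = 80.3% against the stated 80%. Both reproduce. They supply the planned cohort sizes (20 and 10) but do not bear on this point.

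**2. Effect per subject.** One reclassified subject moves a rate by 1/n: 1/20 = 5.0 points, 1/10 = 10.0 points, 1/30 = 3.3 points. With assumed response counts and 95% Clopper-Pearson limits:

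| Group | One rule | Other rule |
|---|---|---|
| Cohort 1 | 10/20 = 50.0% (27.2 to 72.8) | 11/20 = 55.0% (31.5 to 76.9) |
| Cohort 2 | 4/10 = 40.0% (12.2 to 73.8) | 5/10 = 50.0% (18.7 to 81.3) |
| Overall | 15/30 = 50.0% (31.3 to 68.7) | 16/30 = 53.3% (34.3 to 71.7) |

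**3. Direction.**
- PD is a first-event endpoint without confirmation, and 7.10 leaves the baseline value untouched. Dropping post-baseline records can therefore remove a PD or move it later, but cannot create one or bring it forward.
- For BIRR, dropping an unscheduled response can lose a responder. Dropping an unscheduled PD that preceded a response can gain one.

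**4. Constructed subjects (all values assumed).**
- Response: baseline titre 100 RU/mL, lowest scheduled value 55, one unscheduled value 48. Scheduled visits give a 45% reduction, so no response. All records give 52%, so IPR.
- Progression: baseline eGFR 60, scheduled 45, unscheduled 41, titre decline below 10%. Scheduled visits give (60 − 45)/60 = 25.0%, so no PD. All records give (60 − 41)/60 = 31.7%, so PD.

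**5. Does 10.10 settle the matter?** It changes three things at once: it admits unscheduled visits, it removes subjects with 70% or less of the doses or with a relevant IST, and it keeps only the value closest to each target day. For the response example:

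| Day of unscheduled value 48 | Window (target day) | Distance to target | Scheduled rival | Value kept | Result |
|---|---|---|---|---|---|
| 155 | 139–229 (183) | 28 | EOT, Day 169: 14 | EOT | Non-responder |
| 180 | 139–229 (183) | 3 | EOT, Day 169: 14 | Unscheduled | IPR |
| 210 | 139–229 (183) | 27 | EOT, Day 169: 14 | EOT | Non-responder |
| 310 | 230–320 (274) | 36 | FUV, Day 267: 7 | FUV | Non-responder |

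On nominal days C6D1 (Day 141) also falls in the Day 139–229 window, 42 days from target, and loses to EOT. The 11 scheduled post-baseline titres thus become 10. The sensitivity analysis can drop scheduled as well as unscheduled results. PD is not among its visible endpoints.

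**6. Where off-schedule results could matter.** Titre and serum biochemistry are scheduled at all 11 post-baseline visits. Post-baseline 24-hour urine, which Protocol 3.2 requires for the UPCR limb of PD, is scheduled only at C4D1, EOT, FUV and EOS (Days 85, 169, 267, 366). The gaps from Day 1 are 84, 84, 98 and 99 days, about 12 to 14 weeks. A UPCR-based PD found in between needs an extra collection. If that is entered as an unscheduled visit, 7.10 applies to it.

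**The case against.** The strongest reply is that 7.10 already has the right scope. It begins with parameters summarized by visit. The version 5.0 entry in the SAP document history describes the same rule as "unscheduled visits for visit-based analyses will be disregarded, except baseline assessment". SAP 7.11 says that a time-to-event analysis does not need one value per visit. On this reading BIR and PD were never restricted.

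The reading is possible, but the text does not secure it. Response categories (SAP 10.1) and 24-hour urine parameters (SAP 10.2) are themselves summarized by visit, so inputs to BIR and PD fall within the scope sentence. The sentence on unscheduled data carries no limit of its own. SAP 7.11 does not say which records a time-to-event analysis draws on, and BIRR is a proportion. If the main BIRR already used unscheduled results, there would be little reason for 10.10 to announce that the sensitivity analysis does.

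A second reply is that scheduled-only data in the main analysis, with all data in the sensitivity analysis, is a deliberate design. That is a legitimate choice, but it conflicts with the unrestricted definitions, and 10.10 does not isolate the effect.

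Other objections stand. With 11 scheduled titres, a best response resting solely on an unscheduled value should be uncommon. Because PD needs no confirmation, counting every record lets one transient value end the response period. SAP 10.3 to 10.9 are redacted, so a data rule there cannot be excluded.

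Some stronger readings are tempting but not supported:
- That unscheduled results are barred from everything but two displays. Baseline is excepted, and 10.10 uses them for BIRR and other endpoints.
- That the all-visits wording in SAP 10 and Protocol 12.9 directly contradicts 7.10. It mainly contrasts the whole trial with the run-in and treatment phases.
- That the risk comes from 24-hour urine thinning out in follow-up. There are two post-baseline collections up to EOT and two after it.
- That the follow-up gaps explain a subject stopped for PD without PD in the analysis. Dosing is over by then, so that scenario belongs to the treatment phase.

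**Conclusion.** The SAP needs correcting here. The definitions count BIR and PD whenever they occur, while 7.10, taken literally and supported by the implication of 10.10, leaves unscheduled results out of the main derivation. Under that rule PD can only be lowered or delayed, and BIRR can move either way.

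The size is known only per subject: 5, 10 or 3.3 points for n = 20, 10 or 30, assuming that the planned numbers are treated. A reader might go further and put a number on understated PD, for example by supposing that a few of the 30 subjects are affected. The documents give no basis for such a count, nor for calling BIRR biased in one direction.

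The importance is moderate. The trial is descriptive with no hypothesis test, and a one-subject shift is small beside the exact intervals. But the classification of the key secondary endpoint should not depend on which section is read.

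**What to change.** - **SAP 7.10:** limit the exclusion of unscheduled visits to by-visit summaries.
- **SAP 7.13.3 to 7.13.5:** state that BIR, BPR, PD and the time-to-event variables use all scheduled and unscheduled central-laboratory results for titre, serum creatinine/eGFR and albumin, and UPCR from 24-hour urine only, in line with Protocol 3.2. A general phrase covering all central-laboratory results would be too wide, because SAP 11.6.1 also lists spot urine there.
- **Reporting:** footnote the subjects whose BIR or PD rests on an unscheduled record. Show BIRR and PD on scheduled visits only alongside, on the unchanged FAS, so that the effect of these records is seen without the other changes in 10.10.

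The cost is a few sentences, one derivation flag and one extra display. The number of looks will vary by subject, and a single transient unscheduled value could count as PD. The scheduled-only display makes both visible.

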## 7.11. Selection of data in the event of multiple records in a window

Depending on the statistical analysis method, single values may be required for each visit. For example, change from baseline by visit usually requires a single value per visit, whereas a time-to-event analysis would not require on value per visit but rather one value for the study.

Unless otherwise noted in the respective sections, when a single value is needed, the following rules will be used:

- If more than one assessment is assigned to the same nominal visit, select the record closest to the nominal day for that particular visit day
- If there are two assessments that are equidistant from the nominal visit day, the data of the assessment after the scheduled study day will be used

- If more than one assessment is collected on the same day, the latest assessment on that day will be used.

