Sample Size, Planned total number of Clinical Trial Sites and Locations	
Approximately 20 subjects in Cohort 1 and approximately 10 subjects in Cohort 2 will be enrolled and receive MOR202.
 
As this is a Phase Ib/IIa trial primarily conducted to explore safety endpoints, no formal statistical hypothesis has been established for the sample size calculation of this trial.
 
It is expected that approximately 10% of the subjects will prematurely discontinue the trial prior to completion of the last treatment cycle (i.e. end of Week 24).
 
Approximately 55 clinical trial sites in the US, Asia Pacific and Europe will participate in the trial.

Investigational and Control Drug(s) (Name, Description)	MOR202 antibody (compound MOR03087). No comparator drug.
Dose, Route of Administration, Treatment Regimen	9 doses of MOR202 will be administered as an intravenous infusion at 16 mg/kg over 6 treatment cycles of 28-days each. Dosing will occur QW in Cycle 1 and Q4W in Cycle 2 to 6.

Supply, Preparation and Administration	
MOR202 is supplied as a lyophilized powder for reconstitution in labelled glass vials. MOR202 must be stored at 2-8°C until use. For administration, MOR202 will be reconstituted in water for injection (WFI) and diluted into a commercially available 0.9% (w/v) sodium chloride solution.
 
MOR202 will be administered by slow i.v. infusion. Premedication of subjects with antihistamines and antipyretic drugs is recommended. For the first 3 administrations, glucocorticoid premedication is mandatory.

Visit Schedule and Assessments	
Screening: 1 visit
 
Treatment phase: 10 visits, EOT planned after 24 weeks.
 
Follow-up phase: 2 visits, EOS planned 28 weeks after EOT.
 
For details see Figure 1.

Efficacy Assessments	
Proteinuria assessed by UPCR in 24-hour urine and spot urine, anti-PLA2R titer, eGFR.

Special Safety Assessments	
Adverse events will be graded according to National Cancer Institute Common Terminology Criteria for Adverse Events (NCI CTCAE), version 5.

Subject Reported Outcomes / QoL	
CCI [REDACTED]

Pharmacokinetics	
Serum concentrations of MOR202 at selected time points will be assessed for all subjects treated with MOR202 during the course of the trial.

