Serum pregnancy (in FCBP)	X										X	X	X
Urine pregnancy (in FCBP)		X2	X2	X2	X2	X2	X2	X2	X2	X2			
Pregnancy and risk counselling	X												
Hepatitis B/C, HIV Serology/Virology	X												
Urine analysis	X	X2				X2		X2		X2	X		X
24 h urine collection for UPCR ratio, Na +	X	X2						X2			X	X	X
Single urine sample: UPCR ratio#	X	X2						X2	X2	X2	X	X	X
Anti-PLA2R antibodies	X	X2	X2	X2	X2	X2	X2	X2	X2	X2	X	X	X
CBC with differential blood	X	X2	X2	X2	X2	X2	X2	X2	X2	X2	X	X	X
Serum Biochemistry, Immunoglobulins	X	X2	X2	X2	X2	X2	X2	X2	X2	X2	X	X	X
HbA1c	X9												
Coagulation		X2		X				X			X		
Lipid panel	X					X					X		
On site hematology		X2	X2	X2	X2	X2	X2	X2	X2	X2			

Clinical Trial Schedule of Assessments	SC R	BL C1D1	C1D 8	C1D 15	C1D 22	C2D 1	C3D 1	C4D 1	C5D1	C6D1	EOT	FUV	EOS
Day 6	-42 to -1	1	8 ±2 days	15 ±2 days	22 ±2 days	29 ±2 days	57 ±7 days	85 ±7 days	113 ±7 days	141 ±7 days	169 +14 days	267 ±14 days	366 ±14 days
MOR 202 infusion with pre-infusion medication		X	X	X	X	X	X	X	X	X			
PK sampling MGR202 (serum)		X1	X1	X1	X1	X1	X2	X2	X2	X2	X	X	X
PK sampling MGR202 (urine) (spot check) 4		X2	X2	X2		X2	X2	X2	X2	X2	X	X	X
ADA sampling		X2					X2		X2	X2	X	X	X
Biomarker sampling (blood)	X8	X2	X2	X2		X2		X2			X	X	X
Biomarker sampling (serum) 2		X1	X1	X1		X2		X2			X	X	X
Biomarker sampling (urine) (spot check) 3 4		X2	X2	X2		X2		X2			X	X	X

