**CCI**

X1: predose and 30 min after end of infusion;  
 X2: predose, MOR202 may not be applied without baseline UPCR value from 24 h urine collection,  
 X3: postdose;  
 X4: mandatory for all subjects if not done within the last 5 years before start of screening, mandatory for subjects with eGFR < 50ml/min/1.73m^2 or with diabetes mellitus type 2 if not done within the last 6 months before start of screening, optional for all other patients;  
 X5 optional for subjects who had a kidney biopsy at screening,  
 X6: see Section 10.1 of clinical trial protocol,  
 X7: predose during treatment phase, only for subjects who provided optional consent for future research,  
 X8: Only B-cell, T-cell, and natural killer (NK) cell counts,  
 X9: only in subjects with diabetes mellitus type II

SCR: screening, BL: baseline; EOT: end of treatment; FUV: follow-up visit, EOS: end of study

Immune cell counts **CCI**

Antigen specific immunoglobulin levels **CCI**

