**12.11.4. Pharmacodynamic Biomarkers**

Additional PD biomarkers may be identified by assessing the effect of MOR202 on the following biomarkers:

- i. Peripheral blood immune cell populations.

CCI

These biomarkers will be assessed and characterized using descriptive statistics of the following:

- Absolute levels by visit.
- Absolute and relative change from baseline to each visit until EOS.
- Post EOT samples only: Absolute and relative change from EOT visit to each subsequent visits until EOS.

These analyses will be performed on FAS by cohort. Further details will be specified in the SAP.

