## 12.4. Summary Statistics

Summary statistics include n, arithmetic mean, standard deviation (StD), geometric mean, coefficient of variation (CV), median, minimum and maximum. The CV will be expressed as a percentage and calculated as follows:

$$\text{CV of the arithmetic mean (\%)}: \frac{\text{StD}}{\text{mean}} \times 100$$

$$\text{CV of the geometric mean (\%)}: \sqrt{\exp(\text{variance for log transformed data}) - 1} \times 100$$

A table with summaries by cohort and overall, and by study visit will be presented with the following information:

- MOR202 serum concentrations

A table with summaries by cohort and overall will be presented with the following information:

- Terminal elimination half-life (days)

Individual plots of MOR202 serum concentrations over actual sample time with all subjects on the same plot will be generated using linear and semi-logarithmic scales (i.e. log y-axis) by cohort and sampling time (pre-and post-dose).

Figures of mean ( $\pm$  standard error) serum concentrations of MOR202 versus nominal days by cohort will be generated using both linear and semi-logarithmic scales (i.e. log y-axis) and split by pre-dose and 30 minutes post-dose.

MOR202 serum levels may be further analysed performing population PK analyses, which will be reported separately.

Listings of individual serum concentrations and sampling time of MOR202 and individual terminal elimination half-life values will be presented by cohort on PKAS.

The following information will be summarized by arm and overall on PKAS:

Absolute normalized urine levels (i.e. MOR202 urine level/CREA frozen level, both values derived from the same frozen urine sample) by visit

Listings with individual frozen Creatinine values, MOR202 PK samples, and CREA frozen normalized urine levels will be generated by visit on FAS.

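### The SAP's same-day selection rule ignores planned sampling time, so the by-visit serum MOR202 concentration table, read literally, mixes post-infusion values (C1D1 to C2D1) with predose values (C3D1 to C6D1)

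*SAP*

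**What the plan says.** - **Selection rule.** SAP 7.10 covers parameters summarized by visit and refers multiple records for one visit to SAP 7.11. That section opens: "Unless otherwise noted in the respective sections, when a single value is needed, the following rules will be used". Its last rule is: "If more than one assessment is collected on the same day, the latest assessment on that day will be used". Planned sampling time is not mentioned.
- **Sampling schedule.** In Protocol Section 10, Table 2, the serum PK row carries the code X1 at C1D1, C1D8, C1D15, C1D22 and C2D1, and X2 at C3D1, C4D1, C5D1 and C6D1. The footnote reads "X1: predose and 30 min after end of infusion"; X2 is predose only.
- **Concentration table.** SAP 12.4 introduces it with: "A table with summaries by cohort and overall, and by study visit will be presented with the following information". The only item listed is MOR202 serum concentration. Protocol 12.10.2 asks for descriptive statistics by day, which does not settle the sampling time either.
- **Figures and listings.** SAP 12.4 separates pre-dose from post-dose in both the individual plots and the mean plots. It also lists individual concentrations with their sampling times.

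**The concern.** Where two samples are planned on one day, the latest record is always the post-infusion sample. A programmer who follows SAP 7.10 and 7.11 for the SAP 12.4 table would therefore take near-peak values for the first five dosing visits and trough values for the next four. Nothing in the table would show that the quantity had changed.

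Serum concentration after multiple administrations is a named secondary endpoint, and SAP Table 8-1 includes it in both the primary and the final analysis. Two things are at stake in that table. The predose values of the weekly loading phase would not be tabulated. The change from C2D1 to C3D1 would combine a real decline, as dosing moves from weekly to four-weekly, with a switch from post-infusion to predose sampling.

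**Working it through.** The plan states no figure on this point, so there is none to reproduce. The check has two parts.

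**1. What the rule selects.** From Protocol Table 2, serum PK row:

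| Visits | Planned samples | Record kept under SAP 7.11, read literally |
|---|---|---|
| C1D1, C1D8, C1D15, C1D22, C2D1 (5) | predose and 30 min post-infusion | post-infusion |
| C3D1, C4D1, C5D1, C6D1 (4) | predose | predose |

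Split by nominal sampling time, the same data give a predose series at all nine dosing visits and a post-infusion series at five. The C1D1 predose sample precedes any drug, so the informative predose values that the literal table loses are four: C1D8, C1D15, C1D22 and C2D1.

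**2. Illustrative size.** The dosing days (1, 8, 15, 22, 29, 57 and so on) come from Protocol Table 2. The following are assumptions:
- one compartment with first-order decline;
- an equal increment of 1 unit per dose, fully present at the post-infusion sample;
- visits exactly on schedule;
- a half-life t of 7, 10, 14 or 21 days, because the documents give none.

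Formulas:
- q = 2^(−7/t)
- Predose at C2D1 = q + q² + q³ + q⁴
- Post-infusion at C2D1 = predose + 1
- Ratio R = post-infusion / predose at C2D1
- Predose at C3D1 = post-infusion at C2D1 × 2^(−28/t)
- Fall as tabulated (post-infusion to predose) = 1 − 2^(−28/t)
- Fall on predose values alone = 1 − R × 2^(−28/t)

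For t = 7: q = 0.5, so predose at C2D1 is 0.5 + 0.25 + 0.125 + 0.0625 = 0.94 and post-infusion is 1.94. Predose at C3D1 is 1.94 / 16 = 0.12. The tabulated fall is 1 − 1/16 = 94%; the predose fall is 1 − 0.12/0.94 = 87%.

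| Assumed half-life (days) | C2D1 predose | C2D1 post-infusion | R | C3D1 predose | Fall as tabulated | Fall on predose alone |
|---|---|---|---|---|---|---|
| 7 | 0.94 | 1.94 | 2.07 | 0.12 | 94% | 87% |
| 10 | 1.37 | 2.37 | 1.73 | 0.34 | 86% | 75% |
| 14 | 1.81 | 2.81 | 1.55 | 0.70 | 75% | 61% |
| 21 | 2.32 | 3.32 | 1.43 | 1.32 | 60% | 43% |

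Across this range, mixing the sampling times adds about 7 to 17 percentage points to a fall that is already 43 to 87%.

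**The case against.** The strongest reply is that SAP 7.11 is only a default. It applies when one value is needed and the analysis section says nothing different. Its example is change from baseline, whereas the SAP 12.4 table reports concentrations. SAP 12.4 treats predose and post-dose as separate series in both sets of plots, so the table sentence is probably just terse and a split table is probably meant.

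The part about intent stands: a reader might infer a deliberate plan to mix sampling times, and the documents do not support that. But the split is written for the plots and not for the table. If SAP 7.11 is held not to apply, no rule is left, and two records per subject could be pooled at five visits. Only the unwritten split gives an interpretable table.

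Three further limits stand.

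- **The fall is not an artifact.** A reader might call the drop from C2D1 to C3D1 false. On predose values alone it is still 43 to 87% under the assumed half-lives, so mixing only enlarges it.
- **Biomarkers.** Table 2 plans paired serum biomarker samples at C1D1, C1D8 and C1D15, and predose samples on dosing days from C2D1. Protocol 12.11.4 plans "Absolute and relative change from baseline to each visit until EOS". A reader might infer that the early biomarker changes would carry acute infusion and steroid-premedication effects. That cannot be concluded: SAP Section 14 governs those analyses, is largely redacted, and may keep the time points apart.
- **The model is crude.** Protocol 4.2.1 describes a two-compartment model in multiple myeloma patients, with target-mediated disposition likely at lower doses. The percentages above show direction and rough scale; they are not estimates for this trial.

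**Conclusion.** The point holds for one table. SAP 7.11 and 12.4, read literally together, produce a serum MOR202 concentration table that switches from post-infusion to predose values between C2D1 and C3D1. The visit counts, five and then four, follow directly from Protocol Table 2 and need no assumption. The size of the distortion does rest on assumptions: one-compartment decline and a half-life between 7 and 21 days.

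The effect is contained:
- The plots are split by sampling time, and the listings give every concentration with its sampling time.
- Half-life uses actual sampling times (SAP 12.3).
- SAP 7.7 excludes post-dose samples on the first treatment day from baseline.
- Anti-PLA2R, the basis of the key secondary endpoint, is sampled predose on dosing days.
- The primary endpoint, treatment-emergent adverse events, does not use these samples.

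The analysis is descriptive, with no hypothesis testing. This is a minor correction, worth making because a stated rule gives the wrong table if followed. No error is asserted for serum biomarkers.

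**What to change.** - **SAP 7.11:** state that predose and 30-minute post-infusion records are separate analysis time points, and that the same-day rule applies only to repeats within the same planned sampling time.
- **SAP 12.4:** tabulate serum concentrations by cohort and overall, visit and nominal sampling time, giving predose at nine dosing visits and post-infusion at five, as the figures in that section already do.
- **SAP Section 14:** the sponsor should confirm that the redacted text keeps the paired serum biomarker samples at C1D1, C1D8 and C1D15 apart by sampling time. If it does, nothing changes there.

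The cost is about two sentences of SAP wording and one extra stratum in one table. No new data are needed.
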